10.6 Overall Survival

From date of registration to date of death due to any cause. Patients last known to be alive are censored at date of last contact.

10.7 Progression-Free Survival

From date of registration to date of first documentation of progression, symptomatic deterioration (as defined below), or death due to any cause. Patients last known to be alive and progression-free are censored at date of last contact.

Symptomatic Deterioration: The global deterioration of health status requiring discontinuation of treatment without objective evidence of progression.

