7.7 Follow-Up Period

All patients will be followed until 4 years after registration or until death, whichever occurs first.

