## 9.0 STUDY CALENDAR

	PRE-STUDY (w/in 28 days		C	Cycle Length = 28 (+/- 3 days)	days		Off TX	Post Progression FU			
REQUIRED STUDIES	registration, unless otherwise noted)	Cycle 1	Cycle 2	Cycle 3	Cycle 4	Subsequent Cycles up to 24 Cycles	Pre- Progression FU				
PHYSICAL											
History and Physical Exam O	х	Х	Х	Х	Х	Х					
Height	х										
Weight	x	х	Х	х	х	х					
Performance Status	X	Х	Х	х	Х	Х					
Toxicity Notation		X (Days 1, 8, 15, 22)	X (Days 1, 15)	X (Days 1, 15)	X (Days 1, 15)	X (Days 1, 15)	XQ	Xq			
NYHA Assessment	х	х	х	х	х	х	х				
Vital Signs N	х	x	х	х	х	х	x				
Clinical autonomic neurologic evaluation A, H	x	X (every 2 cycles, +/- 7 days)		X (every 2 cycles, +/- 7 days)		X (every 2 cycles, +/- 7 days)	X (every 6 months, +/- 21 days)				
Clinical peripheral neurologic evaluation A, H, K	х	X (every 2 cycles, +/- 7 days)		X (every 2 cycles, +/- 7 days)		X (every 2 cycles, +/- 7 days)	X (every 6 months, +/- 21 days)				
Clinical GI evaluation A, H, K	х	X (every 2 cycles, +/- 7 days)		X (every 2 cycles, +/- 7 days)		X (every 2 cycles, +/- 7 days)	X (every 6 months, +/- 21 days)				
LABORATORY											
Type and screen and blood bank notification E	x										
CBC w/ differential, Platelets C	х	X (Days 1, 8, 15, 22)	X (Days 1, 15)	X (Days 1, 15)	X (Days 1, 15)	X (Days 1, 15)					
Serum Chemistry C, J, K	х	X (Days 1, 8, 15, 22)	X (Days 1, 15)	X (Days 1, 15)	X (Days 1, 15)	X (Days 1, 15)					

	PRE-STUDY (w/in 28 days	PRE-STUDYCycle Length = 28 days(win 28 days(+/- 3 days)					Off TX	Post
REQUIRED STUDIES	registration, unless otherwise noted)	Cycle 1	Cycle 2	Cycle 3	Cycle 4	Subsequent Cycles up to 24 Cycles	Pre- Progression FU	Progression FU
TSH, free T4, free T3 J	х							
HIV, HBV, HCV R	Х							
PT/PTT/INR L, P	X	х	Х	х	Х	X		
RESPONSE ASSESS	SMENT							
Serum β2 microglobulin, LDH, uric acid J	х							
Serum Quantitative Immunoglobulins (IgG, IgA, and IgM)	х							
SPEP with M- protein quantification	х	Х	х	Х	х	х	х	
Serum free kappa and lambda light chains	х	Х	х	Х	х	х	х	
Serum Immunofixation	х	Х	Х	Х	х	х		
Urine Protein Electrophoresis K	х	Х	Х	Х	х	х		
Urine Immunofixation Electrophoresis K	х	Х	х	Х	х	х		
Troponins (T or I) A,L	Х	Х	Х	Х	Х	X	Х	
NT-pro-BNP L	Х	X	Х	Х	Х	X	Х	
Urine or Serum Pregnancy F	x	X	Х	Х	X	X		

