#### 10.0 CRITERIA FOR EVALUATION AND ENDPOINT ANALYSIS

10.1 Measurable disease

For the purpose of measuring hematologic response, measurable disease is defined as:

a. Positive monoclonal serum immunofixation electrophoresis or urine immunofixation electrophoresis,

and/or

- b. Serum free light chain ratio outside of normal range (normal range: 0.25 1.65)
- 10.2 Hematologic Response and Progression

Confirmation must be made by verification on two consecutive determinations.

- a. Hematologic response: (16, 17)
  - Complete Response (CR): CR is defined as laboratory values within the normal range free light chain (FLC) ratio (0.25 – 1.65) and negative serum and urine immunofixation (as per institutional laboratory values).
  - Very Good Partial Response (VGPR): A VGPR is defined as the difference between involved and uninvolved FLCs [dFLC] < 4.0 mg/dL.

  - Partial Response (PR): Partial Response is defined as a dFLC decrease of ≥ 50%, but remaining > 4.0 mg/dL
- b. Hematologic progression: 50% increase from nadir, or from baseline (if there was no response) in any ONE OR MORE of the following: *(18)* 
  - 1. Serum M-protein: 50% increase in Serum M protein to a value greater than 0.5 g/dL.
  - 2. Urine M protein: 50% increase in Urine M protein to a value greater than 200 mg/day (a visible peak must be present)
  - 3. Free light chain increase of 50% to a value greater than 10 mg/dL
- c. Stable Disease: Patients who do not meet criteria for objective response or progression (see Sections 10.2a and 10.2b) will be termed to have stable disease.
- 10.3 Organ Response (19)

Response to therapy in terms of improvement in organ dysfunction will be defined based on functional improvement in one or more involved organ systems. Only 1 parameter is required to satisfy the organ response criteria. In order to be classified as a confirmed organ response, confirmation must be made by verification on a second consecutive assessment at least 4 weeks after the first observation of response.

- a. Liver response requires either:
  - 1. A 50% decrease in (or normalization of, <1.5 IULN) alkaline phosphatase level, or
  - 2. A reduction in the span of the liver by at least 2 cm by radiographic determination.
- b. Renal response is defined as either: (20)
  - 1. A 30% decrease in urine total albumin; or

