11.4 Analysis of Secondary and Other Endpoints

Toxicity will be evaluated using the CTCAE Version 5.0 items. All eligible patients that have initiated treatment will be considered evaluable for toxicity analyses. The maximum Grade for each toxicity will be recorded for each patient, and frequency tables will be reviewed to determine toxicity patterns. Assuming 35 eligible, evaluable patients, any toxicity event seen with at least 5% probability is likely to be observed at least once (83% chance). With 35 eligible patients, response rates and rates of individual toxicities can be estimated to within +/- 17% (95% confidence interval).

Organ response will be evaluated in the subset of patients with evaluable organ involvement using current criteria Organ involvement will be considered evaluable if it qualifies based on the criteria defined in Section 10.3. There may be eligible patients whose organ involvement is based upon a feature (such as amyloid deposition or certain types of soft tissue involvement) that does not have an associated response/progression

definition. These patients will not be evaluated for organ response. The proportion of patients with organ response will be estimated as the number of patients with documented organ response out of the number of patients with documented evaluable organ involvement at baseline.

OS and PFS will be estimated using the Kaplan-Meier method.

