#### f. EVERY 6 MONTHS FOR 4 YEARS AFTER REGISTRATION:

Submit the following:

Follow Up Form

Late Effects Form (if prior to treatment for progression or relapse or a second primary, and prior to non-protocol treatment, the patient experiences any severe [Grade  $\geq$  3] long term toxicity that has not been previously reported).

g. WITHIN 14 DAYS OF SECOND MALIGNANCY:

Submit the following:

Follow Up Form

h. WITHIN 4 WEEKS OF KNOWLEDGE OF DEATH:

Submit the Notice of Death **and a final** S1702 Treatment Form and S1702 Adverse Event (if the patient was still on protocol treatment) or Follow-Up Form (if the patient was off protocol treatment) documenting death information.

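### PFS may be overstated if patients stay in contact without hematologic testing, because Section 10.7 censors at last contact rather than at the last disease assessment

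*Combined protocol and SAP*

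**What the plan says.** Section 10.7 defines PFS as "From date of registration to date of first documentation of progression, symptomatic deterioration (as defined below), or death due to any cause", and adds: "Patients last known to be alive and progression-free are censored at date of last contact". Section 10.6 uses the same date for survival: "Patients last known to be alive are censored at date of last contact". Section 11.4 gives the whole analysis: "OS and PFS will be estimated using the Kaplan-Meier method".

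Hematologic progression (Section 10.2b) is a laboratory finding in serum M-protein, urine M-protein or light chains. The light-chain criterion reads: "Free light chain increase of 50% to a value greater than 10 mg/dL".

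On follow-up, Section 7.7 states: "All patients will be followed until 4 years after registration or until death, whichever occurs first". In the Section 9.0 calendar, the rows for SPEP and for "Serum free kappa and lambda light chains" are marked at every cycle and again in the off-treatment, pre-progression column. No off-treatment interval is attached to either row, whereas several organ tests have six months. Serum immunofixation, UPEP and urine immunofixation are not marked off treatment.

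Section 14.4 requires the AL Follow Up Tumor Assessment Form after each cycle, at discontinuation and at progression. The later submission, "EVERY 6 MONTHS FOR 4 YEARS AFTER REGISTRATION", lists a Follow Up Form and, conditionally, a Late Effects Form. It does not list a tumor assessment form.

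**The concern.** A last-contact date suits survival, because a contact shows whether the patient is alive. It does not suit an event that needs a blood or urine test. A patient who stops testing without progression but answers a six-monthly contact stays in the Kaplan-Meier risk set as event-free until death or the end of contact. Progression in that interval is unlikely to be recorded unless it prompts a test or appears as symptomatic deterioration.

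The plan leaves room for this. Treatment lasts at most 24 cycles, so a large part of the four years is off treatment. Section 7.5 lets patients leave treatment unprogressed through toxicity, delay or completion. After that, a contact date arrives every six months with no form requiring a test result beside it.

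PFS is a named secondary objective of a single-arm study, so it has no internal comparator, and this error runs in one direction.

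**Working it through.** The documents give no PFS assumption, event count or precision, so there is no PFS figure to reproduce. The calculations below are illustrations.

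**Time off treatment.** 24 × 28 days = 672 days; 672 / 30.44 = 22.1 months. Follow-up of 48 months leaves 48 − 22.1 = 25.9 months after a full course, and more after an early stop.

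**Check 1: patients leave testing early but stay in contact.**

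Inputs:
- Median PFS 14 months and median OS 28 months, the pomalidomide figures in Section 2.2. OS 48 months is an assumed alternative.
- Exponential times: PFS rate λ = ln 2 / 14 = 0.0495 per month; death rate μ = ln 2 / 28 = 0.0248 (or ln 2 / 48 = 0.0144).
- A fraction a = 10%, 20% or 30% (assumed) is assigned a leaving time u, uniform over months 1 to 12. All are contacted to month 48 or death, and no later progression is recorded.

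Share who actually leave unprogressed: a × (e^(−λ) − e^(−12λ)) / (11λ) = a × 0.734, which is 7%, 15% and 22%.

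Under last-contact censoring, death is the only event left for these patients. The chance that a patient assigned to leave is counted event-free at 24 months is the mean of e^(−λu) × e^(−μ(24−u)), that is

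e^(−24μ) × (e^(−(λ−μ)) − e^(−12(λ−μ))) / (11(λ−μ)).

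- OS median 28: 0.552 × 0.854 = 0.471. The truth is e^(−24λ) = 0.305. Overstatement = a × 0.167 = **1.7, 3.3 and 5.0 points**.
- OS median 48: 0.707 × 0.801 = 0.566. Overstatement = a × 0.262 = **2.6, 5.2 and 7.9 points**.

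For the median with OS 28, solve (1 − a)e^(−λt) + a × 0.854 × e^(−μt) = 0.5. This gives t = 14.4, 14.9 and 15.5 months, an overstatement of 0.4, 0.9 and 1.5 months.

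**Check 2: a shorter PFS scale.** Section 2.4 reports median PFS 3.7 months for isatuximab in myeloma. Take OS median 18.6 months (one dose group there) and a = 30%. The affected share is 0.3 × 0.351, about 11%. Twelve-month PFS is overstated by 0.3 × (0.639 × 0.421 − 0.106) = 0.3 × 0.163, about 5 points. By simulation the median moves only from 3.7 to 3.8 months.

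**Check 3: with the test calendar built in.** Simulation of 400,000 patients with true median PFS 14 months and true 36-month PFS 17%. Tests run every 28 days to 22 months, then every six months (assumed). A share q stops testing at a uniform time in months 1 to 22, and contact continues to month 48. Median survival after progression is 14 months (assumed). Under last-assessment censoring, deaths count only within six months of the last assessment.

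| q | Median, last contact | Median, last assessment | 36-month PFS, last contact | 36-month PFS, last assessment |
|---|---|---|---|---|
| 0% | 14.7 | 14.7 | 19% | 19% |
| 10% | 14.7 | 14.7 | 20% | 18% |
| 20% | 15.6 | 14.7 | 22% | 18% |
| 30% | 15.6 | 14.7 | 24% | 18% |
| 50% | 17.5 | 14.7 | 28% | 18% |

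At q = 0 the rules coincide. The small excess over the truth there comes from the spacing of tests and affects both rules.

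**Check 4: what the fix must cover.** In the 14-month setting of Check 1, suppose only patients alive at the end are censored at last assessment, while deaths after an untested gap still count at the death date. Then 24-month PFS remains off by 0.2 to 0.5 points (OS 28) and by up to 1.0 point (OS 48). If those deaths are also censored at the last assessment, the result is within 0.1 point of the truth.

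**The case against.** A reader might infer that PFS *is* overstated, or that the plan stops testing once treatment ends. The documents support neither. SPEP and light chains are marked in off-treatment follow-up before progression, so testing is planned, and Section 14.4 asks for a tumor assessment form within 14 days of progression. Untested contact would come from missed or lapsed tests, or from the unstated interval. If the calendar is followed, the rules nearly agree (q = 0 above).

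The affected shares are assumptions, and Check 1 is a severe case: leavers are always contacted and never have progression or symptomatic deterioration recorded later. Either record would shrink the bias.

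The bias is also modest beside sampling error. With 35 patients and 24-month PFS near 30%, the 95% half-width is about 1.96 × √(0.3 × 0.7 / 35) = 15 points. No historical comparison of PFS is planned in Section 11.

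All of this stands, and it limits the size of the point. It does not remove it. Sampling error goes either way and is reported in an interval, while this bias goes one way and is not shown. It could be argued that the words requiring patients to be known progression-free already protect the estimate, but the sentence still sets the date at last contact and does not say what makes that status known.

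**Conclusion.** The point holds conditionally: PFS may be overstated, to the extent that patients remain in contact without hematologic testing. That extent is not in the documents.

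- Scheduled testing done: no material difference between the rules.
- 7% to 22% leaving testing unprogressed in months 1 to 12, true median PFS 14 months: 24-month PFS is high by about 2 to 5 points (OS median 28 months) or 3 to 8 points (OS median 48 months).
- True median PFS 3.7 months, about 11% affected: the median barely moves, but 12-month PFS is high by about 5 points.

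A reader might also infer that the trial's conclusion is at risk. It is not: PFS is secondary and descriptive, and the two-stage decision, sample size and error rates rest on hematologic response. Severity is minor to moderate.

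**What to change.** 1. In Section 10.7, censor patients without documented progression at the last hematologic assessment showing no progression, or at registration if there is none.
2. Prespecify that a death or progression first recorded after a long gap without assessment (for example, more than two scheduled assessments missed) is censored at the last assessment before the gap. Counting missed assessments requires the calendar to state the intended off-treatment interval for SPEP and light chains.
3. Keep last contact for OS, and report PFS censored at last contact as a sensitivity analysis.
4. Record off-treatment SPEP and light-chain assessment dates with the six-monthly follow-up submission, including those showing no progression.

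The cost is a few sentences and one added data item. Treatment, sample size and the primary endpoint do not change. PFS may look slightly less favourable. The new rule assumes that leaving assessment is non-informative, which may fail if patients stop testing because they are getting worse. That is why both versions should be reported. Settling the rule before analysis avoids choosing it after the curve has been seen.

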10.8 Performance Status

Patients will be graded according to the Zubrod performance status scale.

#### POINT DESCRIPTION

- 0 Fully active, able to carry on all pre-disease performance without restriction.
- 1 Restricted in physically strenuous activity but ambulatory and able to carry out work of a light or sedentary nature, e.g., light housework, office work.
- 2 Ambulatory and capable of self-care but unable to carry out any work activities; up and about more than 50% of waking hours.
- 3. Capable of limited self-care, confined to bed or chair more than 50% of waking hours.
- 4 Completely disabled; cannot carry on any self-care; totally confined to bed or chair.

#### 11.0 STATISTICAL CONSIDERATIONS

11.1 Two-Stage Design

The primary goal of this study is to test the hypothesis that the rate of confirmed overall hematologic response (CR+VGPR+PR) to treatment is at most 10% versus the alternative that the true hematologic response rate is 30% or greater.

A two-stage design will be used for patient accrual, with a total of 35 eligible patients who are evaluable for hematologic response per the definition in Section 11.2b below. (24) Patients who received at least one dose of study drug will be considered evaluable. Initially, 20 eligible, evaluable patients will be accrued. If one or fewer hematologic partial or better responses are observed in the first 20 patients, this treatment will be considered insufficiently active in this population and further accrual will be terminated. If two or more confirmed, partial or better responses are observed, then an additional 15 eligible, evaluable patients will be accrued. If at least 8 out of the total 35 patients have a confirmed response, the treatment may be recommended for further testing in subsequent studies. An estimated 39 patients will be enrolled to this study (including 35 eligible and evaluable patients, with 20 enrolled to Stage 1 and 15 enrolled to Stage 2, and with an additional 4 patients enrolled overall to account for ineligible and unevaluable patients).

With an estimated accrual rate of 1-2 patients per month, it is anticipated that the study will reach full accrual in 20 to 40 months.

- 11.2 Sample size and Power Justification
  - a. Assuming the number of hematologic responses is binomially distributed this design has a significance level of 2% and a power of 87% for detecting a true overall hematologic response rate of at least 30% versus the null hypothesis response rate of 10% of less.
  - b. All eligible patients who receive any study treatment will be considered to be evaluable for response and toxicity, and will be included in the analysis.
  - c. Patients who go off study or die prior to the first response assessment will be considered as non-responders.
- 11.3 Analysis of Primary Endpoint

The primary endpoint of this study is overall confirmed hematologic response rate (ORR), which includes partial response (PR), very good partial response (VGPR) and complete response (CR) as defined in Section 10.2.

Hematologic response will be reported with a binomial confidence interval. All eligible patients who received at least one day of treatment, including those that go off study or die prior to the first response evaluation, will be included in the calculation of response rates. The null hypothesis of a response rate of 10% or lower will be evaluated as described above, with potential adjustments to the critical values once the exact number of patients is determined.

11.4 Analysis of Secondary and Other Endpoints

Toxicity will be evaluated using the CTCAE Version 5.0 items. All eligible patients that have initiated treatment will be considered evaluable for toxicity analyses. The maximum Grade for each toxicity will be recorded for each patient, and frequency tables will be reviewed to determine toxicity patterns. Assuming 35 eligible, evaluable patients, any toxicity event seen with at least 5% probability is likely to be observed at least once (83% chance). With 35 eligible patients, response rates and rates of individual toxicities can be estimated to within +/- 17% (95% confidence interval).

Organ response will be evaluated in the subset of patients with evaluable organ involvement using current criteria Organ involvement will be considered evaluable if it qualifies based on the criteria defined in Section 10.3. There may be eligible patients whose organ involvement is based upon a feature (such as amyloid deposition or certain types of soft tissue involvement) that does not have an associated response/progression

definition. These patients will not be evaluated for organ response. The proportion of patients with organ response will be estimated as the number of patients with documented organ response out of the number of patients with documented evaluable organ involvement at baseline.

OS and PFS will be estimated using the Kaplan-Meier method.

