#### 13.0 REGISTRATION GUIDELINES

#### 13.1 Registration Timing

Patients must be registered prior to initiation of treatment (no more than 5 working days prior to planned start of treatment).

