14.4 Data Submission Overview and Timepoints

### a. WITHIN 7 DAYS OF REGISTRATION:

Submit the following:

Onstudy Form

AL Baseline Tumor Assessment Form

Pathology report, confirming AL amyloidosis (as defined in Section 5.1)

If organ involvement was assessed by biopsy, submit the pathology report documenting the involvement (see Section 5.1d).

If patient has involvement of the liver or lymph nodes, submit radiology reports (ultrasound, CT, or MRI) to assess liver and lymph node size at baseline.

See Section 15.0 for specimen submission requirements.

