#### b. WITHIN 35 DAYS AFTER REGISTRATION:

Submit the following:

**S1702** Cytogenetics and FISH Analysis Form.

Institutional Flow Cytometry Report for Immunophenotyping and **S1702** Immunophenotyping Form

Institutional Cytogenetics Report, FISH Analysis Report, and Bone Marrow Aspirate and Biopsy Report

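### The planned toxicity tables count only eligible treated patients, so anyone given isatuximab and later ruled ineligible is left out of them

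*Combined protocol and SAP*

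**What the plan says.** Section 11.4 defines who enters the toxicity tables: "All eligible patients that have initiated treatment will be considered evaluable for toxicity analyses". The tables show the maximum grade of each toxicity per patient. Section 11.2b uses one set for both purposes: "All eligible patients who receive any study treatment will be considered to be evaluable for response and toxicity". The two sections agree. Section 11.1 calls patients with at least one dose evaluable, but it does so within a count of eligible, evaluable patients and refers to 11.2b, so it does not widen the set.

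On numbers, Section 11.1 says "An estimated 39 patients will be enrolled to this study": 35 eligible and evaluable, plus 4 to cover ineligible and unevaluable patients. Section 11.4 quotes, for 35 patients, an 83% chance of seeing at least one case of a toxicity with 5% probability, and a precision of +/-17 percentage points.

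Section 14.1 requires data from all registered patients, including those found ineligible, and says that inadequate documentation generally leads to a ruling of ineligible. Section 13.5 does not allow a registration to be cancelled.

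**The concern.** Eligibility is a reasonable filter for the response set, because the two-stage test concerns a defined population. It does not alter the fact that a patient was exposed to the drug. Evaluating toxicity is secondary objective 1.2a, and the 11.4 tables are its planned analysis. Section 2.2 describes the aim as an efficacy signal without serious toxicity, in what it calls the first study of a CD38 antibody in AL amyloidosis.

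According to 7.1a, infusion reactions are most common at the first administration. A patient who receives one dose and is then ruled ineligible has already been through the period of highest reaction frequency, yet is not counted. Several eligibility limits concern organ function (LVEF, NT-proBNP, creatinine clearance, blood counts in 5.3), so removing patients who fail them need not leave toxicity rates unchanged. The documents do not show which way the rates would move.

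**Working it through.** **1. Can a patient be dosed and then ruled ineligible?**

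- Treatment is planned to start within 5 working days of registration (13.1), that is, day 0 to about day 7.
- The Onstudy and baseline assessment forms are due within 7 days of registration (14.4a). The FISH, cytogenetics and marrow reports are due within 35 days (14.4b).
- Section 7.3 schedules Cycle 1 doses on Days 1, 8, 15 and 22, then Cycle 2 Day 1. Counted from registration, a day 0 start gives doses on days 0, 7, 14, 21 and 28. A day 7 start gives days 7, 14, 21, 28 and 35. Either way, five planned doses fall by day 35.
- If FISH proves not to have been performed, the patient is not eligible (5.3e). If documentation is inadequate, the patient is generally deemed ineligible (14.1).

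So the route exists. Day 35 is the latest due date for the reports, so five doses is the upper end if ineligibility comes to light by then.

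**2. The plan's own figures (11.4, n = 35)**

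- Chance of at least one event at a 5% rate: 1 - 0.95^35 = 83.4% (stated 83%).
- 95% half-width at a 50% rate: 1.96 x sqrt(0.25/35) = 16.6 points (stated 17).
- At a 20% rate: 1.96 x sqrt(0.16/35) = 13.3 points.

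Both stated figures reproduce.

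**3. How far could a tabulated rate move?**

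Let m be the number of dosed-but-ineligible patients. The plan does not give m. If its allowance holds, m is 0 to 4, and part of that allowance covers unevaluable patients. It is not a cap, because 39 is an estimate and accrual runs to 35 eligible, evaluable patients. Section 11.3 likewise leaves the attained number open, "with potential adjustments to the critical values once the exact number of patients is determined". I add m = 6 as an assumed overrun.

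Assume 7/35 = 20.0% is tabulated. If k of the m omitted patients have the event, the all-treated rate is (7 + k)/(35 + m). If their risk is RR times 20%, the expected rate is (7 + m x 0.20 x RR)/(35 + m). RR from 0.5 to 3 is an assumed range.

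| m | none have it (k = 0) | all have it (k = m) | expected, RR 0.5 to 3 | shift, points |
|---|---|---|---|---|
| 1 | 7/36 = 19.4% | 8/36 = 22.2% | 19.7% to 21.1% | -0.3 to +1.1 |
| 2 | 7/37 = 18.9% | 9/37 = 24.3% | not computed | not computed |
| 4 | 7/39 = 17.9% | 11/39 = 28.2% | 19.0% to 24.1% | -1.0 to +4.1 |
| 6 | 7/41 = 17.1% | 13/41 = 31.7% | 18.5% to 25.9% | -1.5 to +5.9 |

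**4. Could a toxicity be missed altogether?**

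An event tabulated as 0/35 could be at most 1/36 = 2.8%, 4/39 = 10.3% or 6/41 = 14.6% among all treated. The chance that a 5% toxicity occurs only in omitted patients, assuming they share that risk, is 0.95^35 x (1 - 0.95^m): 0.8% for m = 1 and 3.1% for m = 4.

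**5. Effect of including them**

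The detection chance 1 - 0.95^n rises from 83.4% (n = 35) to 84.2% (36) or 86.5% (39). The half-width at a 50% rate falls from 16.6 to 15.7 points at n = 39.

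**The case against.** The plan contains no contradiction. The restriction is pre-specified and stated twice. Section 14.1 governs data submission rather than analysis, and the 83% and +/-17% figures are right for 35 patients. Objective 1.2a concerns treatment of relapsed or refractory AL amyloidosis, and a patient ruled out for an unconfirmed diagnosis may not belong to that population.

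Harm in such patients is also not lost to oversight. Expedited reporting needs only one dose (16.1e), and 16.1f adds Grade 3 or higher infusion reactions. The run-in, monthly summaries and six-monthly reports in 11.5 state no eligibility limit. Numbers should be low: waivers are barred (5.0), eligibility is affirmed before registration (13.4b), FISH must be done beforehand, and a FISH without a result still qualifies (5.3e). The upper bounds above need every omitted patient to have the event. At a 20% risk that has probability 0.2^4 = 0.16% for 4 of 4, and with equal risk the expected shift is zero.

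Most of this stands, and it limits the size of the problem. It does not close the gap. The reporting channels serve monitoring, while 11.4 is the planned analysis of the toxicity objective. The point about population supports an eligible-only table as a supplement. It is a weak reason for omitting exposed patients from the main description of harm.

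**Conclusion.** The concern holds. Sections 11.2b and 11.4 both limit the toxicity set to eligible treated patients, the protocol permits dosing before a ruling of ineligibility, and no planned table covers all treated patients. It is a gap in the choice of analysis set; the stated figures are correct.

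The effect is probably small. With 1 omitted patient, an assumed 20% rate shifts by -0.3 to +1.1 points in expectation; with 4, by -1.0 to +4.1. Both are well inside the 13.3-point half-width at that rate. These values rest on the assumed 7/35, the assumed relative risk of 0.5 to 3, and an unknown number of omitted patients. No decision rule is affected: the response rule (11.1) and the run-in pause (11.5) do not use these tables. The change is worth making because it gives a complete account of harm in everyone exposed at almost no cost.

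**What to change.** Split 11.2b. Keep eligible and treated as the response set, on which 11.1 and 11.3 depend. In 11.2b and 11.4, define the toxicity set as every patient who received any isatuximab, regardless of eligibility, and state the denominator of each table. An eligible-only toxicity table can be kept as a supplement. The 83% and +/-17% sentences may be left alone, since they are already conditional on 35 patients. If they are reworded as values for at least 35, do so for toxicity only, because the +/-17% sentence also covers response rates.

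The cost is a few sentences. Section 14.1 already requires the data, and the response rule, significance level and power are unchanged. The one drawback is that toxicity and response denominators may differ by the number of dosed-but-ineligible patients, which clear table labels will handle.
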